#### 9.0 DURATION OF STUDY

The study includes a radical hysterectomy/ radical abdominal trachelectomy with detection of SLN followed by a full pelvic lymphadenectomy along both the UPP and LPP.

The patient may withdraw from the protocol at any time prior to surgery or at any time until retrieval of postoperative data until one year after surgery.

The study is initiated at Lund University hospital with a planned later inclusion of the second investigating center which may motivate a revision of the study protocol related estimated time for enrollment of patients and for accreditation of the second centre and surgeons.

Assuming that the prevalence of pelvic lymph node metastases is 15 % 227 patients will be needed to obtain 34 lymph node positive observations. Given a 95% bilateral detection rate of SLN's approximately 15 patients more will need to be included. On the other hand, ultrasectioning and IHC of SLN's is estimated to increase the proportion of patients with nodal metastases by identifying micro metastases. As there will be a continuous report of node positive patients to the study coordinator an interim analysis will start after 36 node positive patients regardless of the total number of patients included. (see 11, statistical considerations) Accrual will not be suspended during the interim analysis as the intervention is estimated to pose minimal risk to patients and the national treatment protocol, recommending a full lymphadenectomy, will be followed, even in the event of futility.

If the trial continues to stage 2, another 28 node positive patients (total 187 patients) will be required. (see 11, statistical considerations)

Given an estimate that the accrual rate is 2,5 cervical cancer patients per month per center, a total of 45 months will be required to reach 226 cervical cancer patients and a total of an additional 37 months to reach 413 patients.

#### **10 STUDY MONITORING AND REPORTING PROCEDURES**

#### ADVERSE EVENT REPORTING

The study protocol has been revised related principles study monitoring and for reporting adverse events to the principal investigating center after inclusion of the second center.

#### Definitions

An adverse event (AE) is any new medical problem or exacerbation of an existing problem experienced by a subject enrolled in the study, whether or not it is considered drug-related by the investigator.

This study will utilize the Adverse Events Logs (Tables 10.1-5). Any SAE will be reported to the study coordinator [contact] or [contact]

#### Adverse events related to the study drug (ICG).

All adverse events occurring from the first dose of study drug until hospital discharge (whether or not attributed to the study drug) will be reported on the Adverse Event Log. In addition, any adverse event reported by the subject to the investigator after discharge and determined to be reasonably associated with the study drug should also be captured and followed until resolution.

# Adverse events related to the sentinel node procedure as such (excluding AE related the study drug, ICG)

All intraoperative events related to the SLN procedure will be reported on the adverse events log.

# Adverse events related the surgical procedure (excluding the SLN part) including AE until 30 postoperative days.

All adverse events will be reported on the adverse events log.

#### Serious adverse event (SAE):

An adverse event that results in one or more of the following: -Any death occurring prior to the postoperative outpatient evaluation 30 days postoperatively. -Any life-threatening event until and including 30 postoperative days. -Any medical event requiring inpatient hospitalization or prolongation of existing hospitalization beyond five postoperative days

NOTE: Hospitalizations that are not considered SAE are:

-Hospitalization planned prior to first administration of study drug

-Hospitalization for elective treatment of a pre-existing condition unrelated to the study medication

- Hospitalization due to social / practical reasons such as an untimely coordination with local community home care services.

**Attribution:** Attribution is the determination of whether an adverse event is related to a medical treatment or procedure. The categories of attribution are:

Definite: The adverse event is clearly related to the study drug Probable: The adverse event is likely related to the study drug. Possible: The adverse event may be related to the study drug. Unlikely: The adverse event is doubtfully related to the study drug. Unrelated: The adverse event is clearly NOT related to the study drug.

**Unexpected Adverse Event**: An unexpected adverse event is an event not mentioned in the package insert/ manufacturer's instructions or the specificity or severity of which is not consistent with the package insert/ manufacturer's instructions. The grading described beneath and the attribution described above will be used for cathegorization of unexpected adverse events.

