#### **Reporting to the IRB:**

Same criteria as above.

The Study Coordinator will distribute reports which are serious, unexpected and associated with the study intervention (possibly, probably or definitely) to all participating investigators. Copies of all serious adverse event reports will be kept on file the department of Obstetrics and Gynecology, Lund University Hospital.

The study coordinator will also report all individual SAE's related to study drug, the

sentinel node procedure as such, are life threatening or resulting in death (defined above and in table 10.6) to the respective Safety Monitoring Committees (SMC) for clinical studies at Skåne University Hospital or local investigating centre for an independent evaluation.

At any time during the conduct of the trial, if it is the opinion of the investigators that the risks (or benefits) to the patient warrant early closure of the study, this recommendation should be made in writing to the SMC. Alternatively, the SMC may initiate suspension or early closure of the study based on its review of the investigator reports.

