### Sentinel node in cervical cancer Version 1.2 180914 **Table 10. 2. Adverse Events during sentinel node dissection**

STUDY NUMBER	AE/SAE	DESCRIPTION	Grade	Attribution
LU001 examples	AE	Bleeding requiring suture	2	
LU002	AE	Obturator nerve damage	3	

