# Table 10.6 Intraoperative Adverse events will be graded according to the following scale:

Grade	Description
Grade 1	Mild; asymptomatic; not interfering with function.
Grade 2	Moderate; symptomatic; interfering with function but not
	ADL; medical intervention indicated.
Grade 3	Severe; symptomatic; interfering with ADL;
	operative intervention indicated; IV intervention indicated
Grade 4	Life-threatening; major urgent intervention indicated; disabling.
Grade 5	Death

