### Per definitions of SAE and attributions as outlined in protocol

Patients study number				
Date for SAE				
Type of SAE	Yes /no	Attribution		
Death				
Life Threatening				
Drug /ICG related				
Intraoperative related the				
SLN procedure as such				
Intraoperative related the				
full LND/ hysterectomy				
Postoperative				
Unexpected AE				

Description / outcome of the SAE

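### A grade 3 injury during sentinel node dissection, with early discharge and no readmission, is not an SAE under Section 10 and so has no required route to the Safety Monitoring Committee

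*Combined protocol and SAP*

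**What the plan says.** Section 10, under Serious adverse event (SAE), opens with "An adverse event that results in one or more of the following" and lists three outcomes. The first is death before the 30-day outpatient check. The second is a threat to life up to day 30. The third concerns hospital stay: "Any medical event requiring inpatient hospitalization or prolongation of existing hospitalization beyond five postoperative days". After these come only the hospital stays that do not count.

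The route to the SMC is under Coordinating Center Reporting Responsibilities: "The study coordinator will also report all individual SAE's related to study drug". The same sentence extends this to SAEs related to the SLN procedure and to those that are life-threatening or fatal, and it points both to the definition above and to Table 10.6. The investigators may also recommend closure to the SMC in writing, and the SMC may act on its review of investigator reports. The Early Study Closure paragraph rests early closure on the SMC's judgement.

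Table 10.6 describes grade 4 as "Life-threatening; major urgent intervention indicated; disabling". Its grade 3 is severe and symptomatic, limits daily activities, and includes events that call for an operative or intravenous intervention. Table 10.2, the log for SLN dissection, has two sample rows. One is "Obturator nerve damage", marked AE, grade 3.

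The SAE form in Appendix 1 has a row for intraoperative events of the SLN procedure and one for unexpected AEs, under the line "Per definitions of SAE and attributions as outlined in protocol".

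**The concern.** Complications of finding and removing SLNs are a stated objective (Section 1), and Section 8 has them evaluated and reported separately. The SMC route also names the SLN procedure as a ground for independent evaluation. The plan evidently intends an independent body to see serious harm from this step.

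The SAE definition decides which events must be sent to that body, and it is built on death, life threat and hospital stay. A lasting nerve injury may involve none of these. At stake is whether the SMC, on whose judgement early closure rests, is certain to receive severe non-fatal SLN injuries, and whether two centres would classify the same injury alike.

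**Working it through.** The plan states no figure on this point and no arithmetic applies. The check takes an injury during SLN dissection and follows it through the SAE definition, Table 10.6 and the SMC route.

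| Case | SAE criterion met? | Required route to the SMC? |
|---|---|---|
| A. Grade 3, not life-threatening, home by day five, no readmission | None of the three | None stated |
| B. As A, but readmitted for the injury | Third, first limb, on the natural reading | Yes |
| C. As A, but stay prolonged beyond day five | Third, second limb | Yes |
| D. Grade 4 as disabling, not life-threatening, home by day five, no readmission | None listed | Ambiguous |
| E. Life-threatening, or fatal before the 30-day evaluation | First or second | Yes |

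*Case A.* The Table 10.2 nerve example is entered in this way, as AE and grade 3. Being SLN-related does not help, because the SMC sentence selects among events that are already SAEs.

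*Cases B and C.* The third criterion joins two limbs: an event that requires inpatient care, and one that prolongs the current stay. The day-five limit most naturally belongs to the second limb only, so a readmission qualifies. The wording does not settle this, because the limit could be read as applying to both.

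*Case D.* The definition has no disability criterion, yet the SMC sentence refers to Table 10.6, where disabling shares a grade with life-threatening. One reader will say that the reference only describes events already classed as SAEs. Another will say that it brings grade 4 disabling events in. Appendix 1 does not decide between them: it offers a row for SLN intraoperative events but refers back to the protocol's definition.

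For case A, the other channels in the documents are:

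- the AE log, which takes all intraoperative events of the SLN procedure (Section 10);
- the monthly summary by the lead and local investigators and the coordinator, if the event counts as significant (Participating Center Reporting Responsibilities);
- IRB reporting of adverse events under local guidelines, at every centre (Reporting to the IRB);
- separate evaluation of SLN-associated intraoperative events (Section 8);
- review of the full data at the interim analysis by the coordinator, investigators and statistician (Data Management);
- a written recommendation to the SMC, if the investigators judge that risk warrants closure.

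The event is therefore recorded and can be seen. None of these channels requires that it be sent to the SMC.

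**The case against.** The strongest case on the other side is that the event is far from hidden. Adverse events, not only SAEs, go to the IRB under local guidelines. SLN events are evaluated separately, the statistician sees the full data at the interim analysis, and the SMC may act on investigator reports, a phrase not limited to SAEs. All of this stands. A reader might infer that such injuries would be known only from the investigators' monthly summary; the documents contradict that. What remains is that the IRB route depends on local rules, the letter to the SMC is discretionary, and the summary and interim review are done by the study team.

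A reader might also infer that every SLN injury with discharge by day five escapes, or that a disabling injury is plainly excluded. Neither is supported: readmission is naturally its own limb, and the reference to Table 10.6 leaves the grade 4 route open to interpretation.

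Nor do the ureteral and bowel examples in Table 10.4 extend the point. They belong to the hysterectomy or trachelectomy. A non-life-threatening injury there, unrelated to the tracer or the SLN procedure, would not go to the SMC even if classed as an SAE. The bleeding example in Table 10.2 is grade 2.

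Finally, the table rows are only samples, and each log has a column in which SAE could be entered. That is fair, but the gap follows from the definition itself; the sample row only illustrates it. The sentence on who evaluates SLN-related SAEs breaks off in the text available. That is not counted as a defect, and its subject is SAEs in any case.

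**Conclusion.** The point holds in a limited form. There is one definite gap: a grade 3 injury during SLN dissection that is not life-threatening, does not prolong the stay beyond five postoperative days and does not lead to readmission has no required route to the SMC. There is one inconsistency: for a grade 4 disabling injury, the SAE definition, the SMC sentence, Table 10.6 and Appendix 1 do not agree, and the route is ambiguous.

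This rests on reading the SMC sentence as limited to SAEs, which is its plain wording, and on treating inpatient hospitalisation as a separate limb of the third criterion. If the day-five limit applied to both limbs, the gap could be somewhat wider.

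The size cannot be given as a count, because the documents state no rate for such injuries. No endpoint, sample size or error rate is affected. The change is worth making because applying the current rule exactly gives weaker independent oversight of a harm that the study sets out to measure.

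**What to change.** Reconcile the SAE definition, the SMC sentence, Table 10.6, the Table 10.2 example and Appendix 1 as follows.

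1. Add to the SAE definition persistent or significant disability.
2. Add intraoperative events of grade 3 or more attributed to the SLN dissection or the tracer, whatever the length of stay. The attribution scale in Section 10 is worded for the study drug only, so entry in Table 10.2 can identify the dissection events.
3. State that inpatient hospitalisation, including readmission, is a separate criterion from prolongation beyond day five.
4. Change the AE/SAE entry for the obturator nerve example in Table 10.2 to match, and let Appendix 1 refer to the amended definition.

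The reporting route to the SMC stays as it is and would then receive these events.

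The cost is a short amendment to the definition, a corrected example and some additional SAE forms. Because grade 3 includes events that call for an operative or intravenous intervention, some of those forms may concern events managed routinely during surgery. Without a rate in the documents, their number cannot be stated.

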#### **Participating Center Reporting Responsibilities**

#### Reporting to the study coordinator

Any SAE's must be reported to study Coordinator at Lund University Hospital within 3 working days of discovery of the incident, using the study-specific SAE Form. Email: [contact]

The lead and local principal investigators and the study coordinator shall conduct continuous review of data and patient safety for a monthly summary of the included number of patients, patient safety and significant AE's described in the protocol.

All SAE's potentially associated with the study drug, the sentinel node procedure as such or deaths shall be evaluated by a

#### **Reporting to the IRB:**

Each participating center will report adverse events to their IRB per local guidelines.

#### **Coordinating Center Reporting Responsibilities**

Reporting to the study coordinator, Lund University Hospital Same criteria as above.

#### **Reporting to the IRB:**

Same criteria as above.

The Study Coordinator will distribute reports which are serious, unexpected and associated with the study intervention (possibly, probably or definitely) to all participating investigators. Copies of all serious adverse event reports will be kept on file the department of Obstetrics and Gynecology, Lund University Hospital.

The study coordinator will also report all individual SAE's related to study drug, the

sentinel node procedure as such, are life threatening or resulting in death (defined above and in table 10.6) to the respective Safety Monitoring Committees (SMC) for clinical studies at Skåne University Hospital or local investigating centre for an independent evaluation.

At any time during the conduct of the trial, if it is the opinion of the investigators that the risks (or benefits) to the patient warrant early closure of the study, this recommendation should be made in writing to the SMC. Alternatively, the SMC may initiate suspension or early closure of the study based on its review of the investigator reports.

#### 10.1.4. Study Monitoring / study accrual oversight

The study principal investigator, local principal investigator and study coordinator will conduct meetings (teleconferenced) every 6 months to discuss the protocol. The s-PI and l-PI can call a meeting to convene at additional times if deemed necessary, for example following statistical review at the interim period if stopping the study for either achieved goals or futility. Apart from the monitoring described below, the number of node positive patients and potential false negative SLN's will be monitored continuously by e-mail to the study coordinator by the use of the study number assigned to each patient.

In case of identified inconsistencies or missing data, additional source documents (identified only by unique patient number) will be requested from the site to resolve ongoing inconsistencies.

The principal investigator and/or the study coordinator will, if deemed necessary by the principal or second participating center perform audits of informed consents and subject eligibility.

#### **Data Management**

Preoperative, intraoperative and postoperative data from each surgery will be recorded on the standardized study sheets. These study sheets will be made available to each study site. Each study site will be allocated a study number which will serve as the prefix to the case number. For example, Lund university Hospital will be allocated the prefix "1" and the first Sentinel node in cervical cancer Version 1.2 180914 study patient will have the study number "1-001. Each investigating center will hold a record with the full identification of patients whereas data otherwise should only identify the patient by the study number (see above). Upon interim analysis the full data will be monitored by the study coordinator, the principal investigator, local principal investigator and study statistician.

Separate analysis of patient data from individual sites can only be performed with the written permission of the study principal investigator.

**Kommenterad [[name]]:** Staff at the individual centers will be responsible for completing the data collection sheet for each patient and all data will continuously and all be entered into a common secured web-based database (https://data.dynareg.se/slnicgec) using the designated study numbers.

#### **Early Study Closure**

Death will be reported according to section 10.1 above and per local IRB reporting guidelines. The SMC will review all reported deaths monthly. Early closure of the study will be based on judgement of the SMC.

The study will be stopped for futility reasons as described under the statistics section.

### **10.1.8. Protocol Deviations**

Major protocol deviations shall be reported by mail to the study coordinator.

[contact], or [contact] and filed at Lund University Hospital using the designated study number. Major protocol deviations include, but are not limited to, violations to inclusion/ exclusion criteria, erroneous preparation of ICG or surgery by a non-accredited surgeon.

Table 10.1. Adverse Events before docking the robot (during injection of ICG, insufflation, port

placement and adhesiolysis) including conversions to open surgery.

STUDY NUMBER	AE/SAE	DESCRIPTION	Grade	Attribution
Example LU001 Example LU002	AE	Converted, disseminated disea Converted massive adhesions	1	
Example LU002	AE	Converted massive adhesions	1	
	AL	Converted massive adhesions	1	

### Sentinel node in cervical cancer Version 1.2 180914 **Table 10. 2. Adverse Events during sentinel node dissection**

STUDY NUMBER	AE/SAE	DESCRIPTION	Grade	Attribution
LU001 examples	AE	Bleeding requiring suture	2	
LU002	AE	Obturator nerve damage	3	

# Table 10.3. Adverse events during completory pelvic lymphadenectomy

STUDY NUMBER LU001examples LU002	AE/SAE AE AE	DESCRIPTION Bleeding requiring suture or Obturator nerve damage	Grade 2 3	Attribution

# Table 10.4. Adverse events during hysterectomy/ trachelecomy

STUDY NUMBER	AE/SAE	DESCRIPTION	Grade	Attribution
LU001 anomalas		Unstanal damage	3	7 minounom
LU001 examples LU002	AE	Ureteral damage	3	
LU002	AE	Bowel damage	3	

# Table 10.5. Postoperative adverse events until 30 postoperative days (all events)

1			,	
STUDY NUMBER	AE/SAE	DESCRIPTION	Grade	Attribution
LU001 avamplas	AE	Dest homio	3	Autoutoll
LU001 examples LU002	AE	Port hernia Fever of unknown origin	3	
LU002	AE	Fever of unknown origin	2	

# Table 10.6 Intraoperative Adverse events will be graded according to the following scale:

Grade	Description
Grade 1	Mild; asymptomatic; not interfering with function.
Grade 2	Moderate; symptomatic; interfering with function but not
	ADL; medical intervention indicated.
Grade 3	Severe; symptomatic; interfering with ADL;
	operative intervention indicated; IV intervention indicated
Grade 4	Life-threatening; major urgent intervention indicated; disabling.
Grade 5	Death

## Postoperative adverse events will be graded according to the Clavien Dindo classification

Grade I	Any deviation from the normal postoperative course without the need for pharmacological treatment or surgical, endoscopic and radiological interventions Allowed therapeutic regimens are: drugs as antiemetics, antipyretics, analgetics, diuretics and electrolytes and physiotherapy. This grade also includes wound infections opened at the bedside.
Grade II	Requiring pharmacological treatment with drugs other than such allowed for grade I complications.
	Blood transfusionsand total parenteral nutritionare also included.
Grade III	Requiring surgical, endoscopic or radiological intervention
- IIIa	Intervention not under general anesthesia
- IIIb	Intervention under general anesthesia
Grade IV	Life-threatening complication (including CNS complications)* requiring IC/ICU- management
- IVa	single organ dysfunction (including dialysis)
- IVb	multiorgandysfunction

- IVb
- Grade V Death of a patient

